SC NEFROLOGIA E DIALISI PEDIATRICA – TRAPIANTI DI RENE – Direttore: [name]

[contact]

email: [contact]

that biomarkers obtained from liquid biopsies (blood and urine) will improve the stratification and prognosis of INS patients, allowing for accurate tailoring of treatments. As the pathogenesis of the disease is multifactorial, an integrated cellular and secretome multi-omics approach will allow for the identification of biomarkers across multiple levels, to be then validated in the routine clinical setting.

7. Objectives

The **PRIMARY OBJECTIVE** of the **PRECISE** study is the generation of a predictive model to differentiate children with SRNS or SDNS from patients with IRNS at the onset through the integration of -omics, genetic, and clinical data (biomarker signature).

The following **4 SECONDARY OBJECTIVES** will be pursued in the study:

1. Definition of the genetic/epigenetic modifications participating in the pathogenesis of INS.
2. Evaluation of adaptive immune system alterations in INS children.
3. Identification of specific protein patterns in serum and urine in different INS subtypes.
4. Description of the molecular characteristics in healthy children.

8. Methods

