8.1 Study design

Open, multicenter, non-pharmacological observational study.

[figure not shown]
Dipartimento Area Materno - Infatile

SC NEFROLOGIA E DIALISI PEDIATRICA – TRAPIANTI DI RENE – Direttore: [name]

[contact]

email: [contact]

Pediatric Idiopathic nephrotic syndrome

The PRECISE study is an open, multicenter, non-pharmacological biological study. The study will recruit a total of 310 INS patients and 40 controls. In details, the study will recruit 110 treatment-naïve childhood INS patients as a discover cohort, who will be followed for 12 months. At enrolment urine and blood samples will be collected as for normal clinical practice for the planned analysis. At the 12-month follow-up, patients will be classified according to international guidelines as steroid-dependent (SDNS)/frequent relapsing (FRNS) and infrequent relapsing nephrotic

Dipartimento Area Materno - Infatile

SC NEFROLOGIA E DIALISI PEDIATRICA – TRAPIANTI DI RENE – Direttore: [name]

[contact]

email: [contact]

syndrome (IRNS) (10). Additional assessments and biological samples will be performed according to the study flowchart and as described in the study procedure chapter. A homogeneous control group (n=40) by age of children undergoing sampling for minor urological surgical correction procedures will be also enrolled. In the validation phase, biological samples from an independent group of prevalent INS (200 cases) cases will be collected.

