SC NEFROLOGIA E DIALISI PEDIATRICA – TRAPIANTI DI RENE – Direttore: [name]

[contact]

email: [contact]

activation of specific signaling cascades by posttranslational modification (phosphorylation) we will also characterize the phospho-proteome. Phosphorylated peptides are enriched after standard isolation and purification with a special kit (High-Select Fe-NTA Phospho-peptide Enrichment Kit). For an unbiased serum proteomics approach, we can rely on the established fully automated clinical pipeline using liquid handling robots and state-of-the-art mass spectrometry platforms, including the latest generation Orbitrap Exploris 480. The approach enables the detection and quantification of on average 300 plasma/serum proteins per hour using a data-independent acquisition approach from a 5 µl sample volume.

12. Source Documents

Medical history and all clinical data collected during the study will be collected from each visit's medical records.

Local laboratory records will be used to collect laboratory analysis results.

13. Sample Size

As this is a descriptive and explorative study without inference in the primary endpoint, and given the incidence of childhood idiopathic nephrotic syndrome, which is considered a rare disease, the number of recruiting centers, we foresee enrolling in this study 110 treatment-naïve INS children. A homogeneous age control group of healthy children undergoing minor urological surgical corrections will be enrolled as a control group (n=40 children in 3 years). These numbers are the maximum we can recruit, but at the same time, we think that this study could serve as an important basis for appropriate studies in the future.

14. Data Management

A consortium was created under the direction of the Lead Unit (IRCCS Ca Granda of Milano, [name], Proposal Coordinator) with the Partners involved in the study. At the enrollment visit, a unique code will be assigned to each participant. The de-identification of the data will take place in such a way that people who access the database will not be able to trace the identity of the subjects in any way. Only local investigators will be able to trace the identity of the enrolled subjects.

The data necessary for the study will be recorded in a specific eCRF in a Data Management System validated according to national legislation, provided by the Scientific Management of the Foundation. The platform used will be RedCap (Research Electronic Data Capture).

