15.1 Primary endpoints: analysis

Statistical analysis using linear mixed effect models will ensure that data from the same individuals over time are properly considered. Network-based analysis using a linear mixed effect model LASSO implementation will allow us to identify key features associated with various clinical endpoints. To identify subsets of features, across all OMICs, associated with disease progression and treatment response, we will use a genetic algorithm-based feature selection approach. Unlike LASSO, this approach can identify non-linear relationships between features and can be linked to almost any predictive modeling approach. The feature subsets will further be evaluated in already available public domain data and then applied to a much larger cohort within the PRECISE consortium.

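### Section 15.1 checks the selected features only outside the 110 onset children, and the one validation cohort described cannot estimate discrimination at onset, which is the primary objective

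*Protocol*

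**What the plan says.** Section 7 gives the primary objective as the "generation of a predictive model to differentiate children with SRNS or SDNS from patients with IRNS at the onset". Section 8.1 says that "the study will recruit 110 treatment-naïve childhood INS patients as a discover cohort, who will be followed for 12 months". Section 9.1 requires no previous treatment for INS, and Schedule A places their first samples at onset.

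Section 15.1 describes a mixed-model LASSO and then a genetic algorithm: "To identify subsets of features, across all OMICs, associated with disease progression and treatment response, we will use a genetic algorithm-based feature selection approach". It adds that this approach "can be linked to almost any predictive modeling approach". The next step is: "The feature subsets will further be evaluated in already available public domain data and then applied to a much larger cohort within the PRECISE consortium".

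Section 8.1 describes a validation phase with 200 independent prevalent cases. Section 10.1 and Schedule C enrol them at relapse and sample them again at remission. Section 9.3 asks for a previous diagnosis and sets no condition on earlier treatment. Section 13 justifies the numbers by feasibility: "As this is a descriptive and explorative study without inference in the primary endpoint".

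**The concern.** The stated validation route does not match the stated objective. The objective concerns untreated children at first presentation. Among the study's own patients, only the 110 are sampled in that state. The prevalent cohort is sampled at a different stage of disease and possibly after treatment, so its AUC answers another question.

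An honest at-onset figure from this study's own samples must therefore come from within the 110. Section 15.1 has no step for that: no hold-out, no resampling and no other control of optimism. A search over many omics features in 110 children will find a subset that separates the classes by chance. If performance is quoted from the children used for the search, it will be far too high, and features may go forward to validation for that reason alone.

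**Working it through.** **Figures in the protocol.** It states no power calculation and no performance figure, so there is none to reproduce. The cohort arithmetic agrees: 110 + 200 = 310 INS patients (section 8.1). If the larger cohort of section 15.1 means the 200 prevalent cases, the ratio is 200/110 = 1.8.

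**Cohorts side by side.**

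| | Discovery (9.1, Schedule A) | Prevalent (9.3, 10.1, Schedule C) |
|---|---|---|
| Number | 110 | 200 |
| First sample | onset | relapse |
| Untreated required | yes | no |
| Matches the section 7 objective | yes | no |

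**Simulation inputs.**
- n = 110 (section 8.1).
- Candidate features p = 300, 2,000 or 20,000. This is an assumption. The low value matches the roughly 300 serum proteins that section 11 gives for one platform.
- Signature size k = 5, 10 or 20. This is an assumption.
- SRNS/SDNS share 30% or 50%. This is an assumption: section 6 gives 10–20% for SRNS and nothing for SDNS.
- All features are independent standard normal and unrelated to outcome, so the true AUC is 0.5.

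**Method.** A genetic algorithm (population 80, 60 generations, linear-model fit as the criterion) chose a set S of k features. The score was s = b0 + Σ b_j x_j over j in S, and AUC = P(s in a case > s in a non-case). There were 16 runs per setting. AUC was measured in-sample, by 5-fold cross-validation after selection on all 110, by 5-fold cross-validation with the whole search repeated in each fold, and in 200 fresh subjects.

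Mean AUC on pure noise (30% share / 50% share):

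| p | k | In-sample | CV after selection | Selection inside folds | 200 fresh |
|---|---|---|---|---|---|
| 300 | 5 | 0.852 / 0.830 | 0.819 / 0.799 | 0.508 / 0.514 | 0.514 / 0.508 |
| 300 | 10 | 0.931 / 0.920 | 0.877 / 0.871 | 0.500 / 0.531 | 0.503 / 0.524 |
| 300 | 20 | 0.984 / 0.971 | 0.935 / 0.905 | 0.501 / 0.493 | 0.488 / 0.506 |
| 2,000 | 5 | 0.892 / 0.863 | 0.859 / 0.827 | 0.489 / 0.503 | 0.514 / 0.483 |
| 2,000 | 10 | 0.963 / 0.948 | 0.932 / 0.914 | 0.505 / 0.524 | 0.504 / 0.505 |
| 2,000 | 20 | 0.995 / 0.990 | 0.976 / 0.951 | 0.530 / 0.496 | 0.498 / 0.504 |
| 20,000 | 5 | 0.893 / 0.874 | 0.867 / 0.847 | 0.497 / 0.463 | 0.504 / 0.512 |
| 20,000 | 10 | 0.966 / 0.958 | 0.938 / 0.925 | 0.503 / 0.488 | 0.496 / 0.499 |
| 20,000 | 20 | 0.996 / 0.995 | 0.973 / 0.966 | 0.519 / 0.501 | 0.476 / 0.492 |

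Optimism (in-sample minus fresh) runs from 0.830 − 0.508 = 0.32 to 0.996 − 0.476 = 0.52. The same number of features taken at random gave in-sample AUC 0.62–0.77, so much of the inflation comes from the search.

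**Sensitivity.**
- With leave-one-out cross-validation as the search criterion (150 generations, 40% share, 6 runs per setting), the reported AUC was 0.80–0.99 and the AUC in fresh subjects 0.47–0.52.
- A shorter search (population 40, 40 generations, ridge classifier, 44 versus 66 children, 12 data sets, p = 2,000, k = 10) gave in-sample AUC 0.90 (range 0.85–0.94) and 0.50 in new children.

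**The case against.** The strongest reply is that section 15.1 names families of methods, and that folds, tuning and model locking belong in a SAP that is not shown. That is fair for the details. It does not cover the main point, because the protocol itself states a validation route and that route does not fit the objective. A SAP that added only ordinary cross-validation would not repair it, as the table shows.

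A second reply is that external testing is planned, so a noise signature should fail there. This is right, and it rules out the reading that a useless signature could never be told from a real one. But failure in relapse samples would be ambiguous, since a genuine onset signature might fail there too. Success there would still give no at-onset accuracy.

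Other stronger readings are also unsupported:
- A reader might infer that all 110 children are used for selection and that only an in-sample figure will be reported. The protocol says neither. It is silent on resampling and names no performance measure.
- A reader might infer that no other onset data exist. The public data are not described and might include onset samples.
- A reader might expect near-perfect AUC from noise. An AUC of about 0.95 or more needed roughly 10 features with p of at least 2,000, or 20 features. With 5 features it was 0.83–0.89. Real omics features are often correlated, which lowers the effective number searched.
- A reader might conclude that the signature will be mostly noise. A simulation without signal cannot show what share of a real signature is noise.

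**Conclusion.** The point holds in this form: followed as written, section 15.1 yields no unbiased estimate of at-onset discrimination from the study's own 110 children, and the one validation cohort described cannot supply it. On noise, the optimism to guard against is about 0.3 to 0.5 on the AUC scale. This rests on the assumed signature size, feature count, class share and independent features, but the direction was the same in every setting tried.

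The exploratory label in section 13 lowers the severity without removing the defect, because a descriptive AUC is biased by selection as much as a tested one. This is a should-fix point, to be settled before any feature selection starts.

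**What to change.** Amend section 15.1 to state that:

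1. Imputation (including the random-forest step of section 17), scaling, LASSO or genetic-algorithm selection, and tuning are all repeated inside every fold of repeated nested cross-validation of the 110 onset samples, with folds stratified by class.
2. The outer-fold AUC with a 95% CI is reported as the at-onset performance.
3. The final model and its cut-off are locked before they are applied to the validation cohort.
4. The prevalent-cohort result measures transport to relapse samples, not accuracy at onset.

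A label-permutation null and a summary of selection stability are useful but optional.

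The cost is wording and computing, with no new patients or samples. The reported AUC will be lower than an in-sample figure, and its interval will be wide. As a rough guide with 44 versus 66 children (assumed), the standard error at AUC 0.5 is √[(110 + 1)/(12 × 44 × 66)] = 0.056, a half-width of 1.96 × 0.056 = 0.11.

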15.2 Secondary endpoints: analysis

Differences between two groups of patients for all the analysis conducted will be evaluated using Student's parametric T-test (in case of normality of variables distribution and homoscedasticity of variance) or Mann – Whitney's non-parametric test. The normality of the data will be evaluated by the Shapiro-Wilk test and the homoscedasticity assumption of the variance will be evaluated by the Hartley F-max test. In cases where more features are available than samples, regularized regression approaches, such as LASSO, or feature selection approaches will be used to identify potential combinations of features associated with a given outcome. Analyses of differences in continuous outcome measures between 3 or more levels of categorical features will take place through analysis of variance (ANOVA) using multiplicity-adjusted post-hoc tests by Dunnett or Tukey, as appropriate. Data analysis will be performed using GraphPad Prism software and P-values of 0.05 will be accepted.

16. Quality control

Only after the approval from ethics committee and regulatory authorities, centers will enroll patients who meet inclusion and exclusion criteria and will propose them to participate to the study signing the informed consent. The coordinating center will have access to all registered data to verify any anomalies and report them to the participating center. All data will be handled, registered, and reported in accordance with the good clinical practice. As Promoter, Fondazione IRCCS Ca' Granda Ospedale Maggiore Policlinico can carry out a quality check on the study at its discretion. In this case, the investigator should allow the monitor to directly access all relevant documentation and devote some of his or her staff time to the reviewer to discuss the results of the monitoring and any other aspects of the study. In addition, the regulatory authorities can carry out inspections. In

Dipartimento Area Materno - Infatile

SC NEFROLOGIA E DIALISI PEDIATRICA – TRAPIANTI DI RENE – Direttore: [name]

[contact]

email: [contact]

this case, the investigator must authorize the inspector direct access to all relevant documentation and devote part of his time and his staff to the inspector himself to discuss the results of the monitoring and any other aspects of the study.

17. Study limitation

This study is a pilot study and shows some risks associated with it. The following limitations can be highlighted:

1. Due to the nature of the pathology (rare disease), one of the risks could be not reaching the number of recruited patients (annual incidence of 2-7/100,000 children). Our contingency plan will be the integration of additional ERKnet and ESCAPE Network centers through an addendum to the protocol.
2. The other limitation could be the absence of sample stability. Our contingency plan will be to define specific isolation workflow protocols, centralize the biobanking system, and perform sample stability tests for the different applications.
3. Another problem could be a difficult blood draw based on the age of the new-onset children recruited in the study. We will exclude Infantile N from the study to overcome this problem.

From the statistical side, all the data will be extensively scrutinized to ensure that misreporting is minimized. Potential confounders will be identified and assessed routinely throughout the analysis. Where possible, confounding factors will be adjusted for in the analysis. Where < 10% of missing data are present in a variable we will aim to impute missing data from other available data sources using a random Forest regression or classification approach. Variables with >20% missing values within a group will be kept aside and used only for descriptive quantitative evaluations. Statistical analysis using linear mixed effect models will ensure that data from the same individuals over time are properly considered.

18. Other aspects

The study will be conducted by the Standards of Good Clinical Practice, the ethical principles deriving from the Declaration of Helsinki.

The study and the related documentation will be presented to the competent Ethics Committee of each center. The study will begin only after receiving the authorizations requested according to the institution's internal procedures.

The Ethics Committee must also approve any changes to the protocol and advertising used to recruit subjects for the study, according to local regulations.

18.1 Informative note to subjects and consensus module to personal data treatment.

The investigators have the responsibility to obtain a signed informed consent by parents or legal

Dipartimento Area Materno - Infatile

SC NEFROLOGIA E DIALISI PEDIATRICA – TRAPIANTI DI RENE – Direttore: [name]

[contact]

email: [contact]

guardians before collecting data. Signed documents must be stored by the investigators and a copy must be given to them. Parents, legal guardians or patients (if = 18 years old) will have all the time necessary for the evaluation of the information received before providing their informed consent to the use of sensitive data of minors. The investigator will have to obtain spontaneous informed consent from them before using it in any way for the study. The written consent to the handling of sensitive data must be subscribed by the date and signature of parents, legal guardians or patients (if = 18 years old) and by the investigator or his representative. The investigator has to give to them a signed copy of informed consent; the original form will be retained with the other documents of the study protocol; the module for the acquisition of informed consent to the treatment of sensitive data will be attached to the clinic folder.

The Principal Investigator guarantees that the data of the patients enrolled during the study will be kept, archived, and processed in full compliance with the regulations on privacy under art. 13 of Regulation No. 2016/679/EU and the national privacy legislation in force, the Code of Ethics regarding data processing for statistical-scientific purposes, and the "Guidelines for the processing of personal data in the context of clinical trials of medical products" published in the Gazzetta Ufficiale n. 190 of 14 August 2008.

Patient data will be accessible only to internal and external personnel specifically appointed and bound by an obligation of secrecy in relation to any information learned during the study.

The Principal Investigator also guarantees that he has implemented the minimum security measures required by the aforementioned legislation for data processing using electronic and non-electronic tools, in order to avoid illicit data processing.

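### Section 15.2 provides no test that allows for unequal variances, so if variances differ between these unequal groups the secondary comparisons can miss the 5% level in either direction

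*Protocol*

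**What the plan says.** Protocol section 15.2 sets the tests for the secondary endpoints.

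- **Two groups:** "Student's parametric T-test (in case of normality of variables distribution and homoscedasticity of variance) or Mann – Whitney's non-parametric test".
- **Pre-tests:** Shapiro-Wilk is named for normality. For equal variances, the section says: "homoscedasticity assumption of the variance will be evaluated by the Hartley F-max test". The level of each pre-test and the degrees of freedom for F-max are not given.
- **Three or more groups:** comparison "will take place through analysis of variance (ANOVA) using multiplicity-adjusted post-hoc tests by Dunnett or Tukey, as appropriate". No alternative is named if an assumption fails.
- **Threshold:** "P-values of 0.05 will be accepted".

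Endpoints 3, 4, 6, 7 and 8 in section 8.3 each compare SRNS/SDNS, IRNS and healthy children, so they fall under the three-group rule. On sizes, section 8.1 states that "the study will recruit 110 treatment-naïve childhood INS patients as a discover cohort" and sets the control group at 40. The split of the 110 into SRNS/SDNS and IRNS is not given, and neither is any SD.

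**The concern.** The section sees that variances may differ, since it tests for that, but what follows does not deal with it.

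- For two groups, a failed variance check leads to Mann-Whitney. That test does not hold its level for a difference in location when the spreads differ and the groups are unequal in size.
- For three groups, ordinary ANOVA pools the variances, and nothing is said about what to do if they differ.
- The check itself is a poor fit. Hartley's F-max takes its critical value from equal group sizes, and the design fixes 40 controls against 110 patients in total.

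At stake is whether a P-value below 0.05 in a secondary comparison means what it says. If a small group is the more variable one, false positives rise. If a large group is, real differences are missed, in a study whose section 13 describes its numbers as the most that can be recruited.

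**Working it through.** **Inputs from the protocol.** 110 incident patients and 40 controls (8.1); threshold 0.05 (15.2), taken as two-sided; SRNS 10–20% of patients (section 6), which is 11–22 of 110 before SDNS is added.

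**Assumptions.** SRNS/SDNS vs IRNS of 40 vs 70 or 20 vs 90; SD ratios of 1 or 2; normal data with equal means; pre-tests at 0.05. The protocol states no error or power figure beyond 0.05, so there is none to reproduce first.

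**1. F-max with equal variances, 110 vs 40.** The statistic is the larger sample variance over the smaller. It rejects above c = F(0.975; ν, ν). Its true size is P[F(109,39) > c] + P[F(39,109) > c].

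| ν taken from | c | True size | Simulated |
|---|---|---|---|
| smaller group, 39 | 1.891 | 1.8% | 1.9% |
| mean size, 74 | 1.583 | 8.5% | 8.9% |
| larger group, 109 | 1.459 | 15.6% | 16.2% |

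The nominal 5% thus becomes about 2% to 16%, depending on a choice the protocol leaves open. A variance-ratio test with the correct degrees of freedom gives about 5%.

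**2. Mann-Whitney when spreads differ.** For normal groups with equal means, sizes m and n and SDs σx and σy:

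- True variance of U/(mn) ≈ a/m + b/n, where a = arcsin[σx²/(σx²+σy²)]/2π and b = arcsin[σy²/(σx²+σy²)]/2π.
- Variance assumed by the test = (m+n+1)/(12mn).
- Error ≈ 2[1 − Φ(1.96/√r)], where r is true over assumed variance.

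For an SD ratio of 2:1, a = arcsin(0.8)/2π = 0.1476 and b = arcsin(0.2)/2π = 0.0320. For 40 vs 70 with the smaller group more variable, the true variance is 0.1476/40 + 0.0320/70 = 0.00415, against an assumed 111/33,600 = 0.00330. So r = 1.255 and the error is 8.0%. The other cases follow in the same way. The last column is the full rule as written, simulated with 10,000 data sets (standard error about 0.2 to 0.3 points); ranges are from repeat runs.

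| Sizes | More variable group (SD 2x) | r | Mann-Whitney, formula | Full rule, simulated |
|---|---|---|---|---|
| 40 vs 70 | smaller | 1.255 | 8.0% | 7.7–8.7% |
| 20 vs 90 | smaller | 1.505 | 11.0% | 11.8–12.5% |
| 40 vs 110 | smaller (controls) | 1.392 | 9.7% | 9.6–10.1% |
| 40 vs 70 | larger | 0.881 | 3.7% | 3.7% |
| 20 vs 90 | larger | 0.631 | 1.4% | 1.2% |
| 40 vs 110 | larger (patients) | 0.749 | 2.4% | 2.3–2.5% |

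With equal SDs the full rule gives 5.0–5.6%. Welch's t-test gives 4.6–5.6% throughout.

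**3. How much is due to F-max?** Replacing it by the correct variance-ratio test moves the error from 12.5% to 11.8% (20 vs 90) and leaves it at 10.1% (110 vs 40). The fallback test drives the error, not the gate.

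**4. Ordinary ANOVA.** The pooled variance is Σ(nᵢ−1)σᵢ²/(N−3).

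- At 20/90/40 with SDs 2/1/1 it is (19×4 + 89 + 39)/147 = 204/147 = 1.388. ANOVA therefore takes the variance of the smallest group's mean as 1.388/20 = 0.069, when it is 4/20 = 0.200.
- At 40/70/40 with SDs 2/1/1 it is (39×4 + 69 + 39)/147 = 264/147 = 1.796, giving 1.796/40 = 0.045 against a true 0.100.

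Simulated error, 20,000 data sets each:

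| SDs (SRNS/SDNS, IRNS, controls) | 40/70/40 | 20/90/40 |
|---|---|---|
| 1/1/1 | 5.0% | 4.9% |
| 2/1/1 | 8.6% | 16.2% |
| 1/2/1 | 2.5% | 0.8% |
| 2/2/1 | 4.2% | 4.0% |

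Tukey-Kramer does not rescue the 2/1/1 cases (familywise 8.6% and 16.8%). Welch's ANOVA gives 4.7–5.4% throughout.

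**5. Power, simulated.** With 40 controls at SD 1, 110 patients at SD 2 and a difference of 0.7, the stated route has about 65–67% power and Welch 80%. With equal variances, Student against Welch is 76.8% vs 76.2% (40 vs 110) and 80.4% vs 78.5% (20 vs 90).

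**The case against.** Several points on the other side carry weight.

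- **Unequal sizes alone do no harm.** A reader might infer that the error rates are wrong simply because the groups are unequal. The figures do not support that: with equal variances the rule and ANOVA hold about 5%, and the protocol gives no SD that shows otherwise.
- **F-max is not the main fault.** It is the most visible flaw, but correcting it changes almost nothing.
- **It is tempting to say that the smaller, sicker group inflates the error.** Against 110 patients the smaller group is the healthy controls. The 10% figure there needs controls to be twice as variable as patients. If patients are the more variable, that comparison is conservative. If both patient groups have twice the control SD, ANOVA is near 4%.
- **No endpoint clearly asks for a pooled 110 vs 40 test.** The endpoints named above have three groups, and the two-group sentence speaks of patients. The total in "a total of 310 INS patients and 40 controls" includes 200 validation cases, so it does not give the sizes compared.
- **20 vs 90 is a low-end split,** because SRNS alone may be 11–22. At an even 55 vs 55 with SD 2x, the two-group rule gives 5.8–6.0%.
- **The variance check may be meant to cover ANOVA too.** It is not expressly limited to two groups. Only the absence of any resulting action is firm.
- **Mann-Whitney may validly reject when distributions differ only in spread.** It is an error only if the question is one of location, as it is for endpoints framed as differences in concentration, cell percentage or mean size.

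The study's exploratory label, and the possibility of a separate analysis plan, limit the severity. They do not remove the point: section 13 disclaims inference for the primary endpoint only, and section 15.2 itself names the tests and the threshold for the secondary ones.

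**Conclusion.** The point holds in a conditional form. Section 15.2 has no method that allows for unequal variances, and neither the Mann-Whitney switch nor ordinary ANOVA makes up for that. If variances are equal, about 5% is kept. If the smallest group has twice the SD, error is about 8–12% for the two-group rule and 9–16% for ANOVA over the two assumed splits. If the largest group has twice the SD, it is about 1–4%, with power lost. These sizes rest on assumed splits, assumed SDs and normal data; skewed data were not simulated. F-max is ill-suited to unequal groups but is a side issue. Only exploratory secondary comparisons are affected, so this is a modest correction that should be made, not a threat to the study.

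**What to change.** In section 15.2, drop the F-max gate and name methods that allow for unequal variances from the start:

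- **Two groups:** Welch's t-test.
- **Three or more groups:** Welch's ANOVA with an unequal-variance post-hoc test such as Games-Howell, in place of Dunnett or Tukey.
- **Skewed measures:** analyse on the log scale, with the scale for each measure fixed in advance.
- **Sensitivity analyses:** Mann-Whitney or Kruskal-Wallis, described as comparing distributions.

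The cost is one paragraph of wording. If variances turn out equal, the loss of power is 0.6 points at 40 vs 110 and 1.9 points at 20 vs 90. No change to recruitment, sampling or visits is needed.
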